The investigator should assess the benefit-risk of continued AR101 treatment when a subject has several AR101-related systemic allergic reactions (anaphylactic events) during maintenance treatment. AE, adverse event; BIW, twice weekly; QD, once daily; QOD, every other day; QOW, every other week; QW, once weekly; SAE, serious adverse event.

- This study period consists of the subject receiving the 300 mg dose of study product QD, QOD, BIW, QW, or QOW. For any noted symptoms during the QD Initial Maintenance or Extended Maintenance period, the same study product dosing guidelines and procedures for QD dosing will be followed as for the Up-Dosing Period. However, for subjects on nondaily regimens, the following guidelines and procedures apply. The investigator should assess the benefit-risk of continued AR101 treatment when a subject has several AR101-related systemic allergic reactions (anaphylactic events) during maintenance treatment.
- The tolerability of doses on nondaily dosing regimens will be evaluated as in Section 6.8 and Table 10. In the event of a clinically significant intercurrent AE occurring at the time of a scheduled QOD, BIW, QW, or QOW dose, subjects should be advised to hold the scheduled dose until the AE is resolved and the dose can be safely administered; the interval between doses should be reset once the subsequent dose is tolerated. *If the dose must be held for > 3 days past when the dose was due to be taken*, the investigator must discuss the case with the sponsor's medical monitor prior to administering the next dose. Options available at that time include, but are not limited to, any of the following:

- ARC008 Protocol Amend 6.0
- 1. Continue the same Treatment Pathway and administer the next 300 mg dose under supervision at the study site.
 - a. If tolerated, continue EM dosing at 300 mg on the same schedule, resetting the dosing interval;
 - b. If not tolerated, consider options 2 or 3 below.
- 2. Continue the same Treatment Pathway and administer approximately half of the 300 mg dose under supervision at the study site. The entire 300 mg dose should be prepared with the preferred vehicle and then approximately half of the dose should be administered; the remainder should be discarded. If not tolerated, the subject should be discontinued from the study. If tolerated, up to 3 successive doses can be administered this way according to the subject's assigned schedule, but then 300 mg should again be attempted.
- 3. Discontinue Treatment Pathway 1 and switch to Treatment Pathway 2, initiating the dose reduction and modified escalation procedure described in Section 7.2.2. This should be the preferred option for any QOD, BIW, or QW subject who had missed 4 or more scheduled doses and/or whose interval between AR101 exposures exceeds 14 days.
- 4. Discontinue ARC008.
- For subjects having acute reactions to QOD, BIW, QW, or QOW doses, the next action will be determined by symptom severity. As mentioned in Section 3.1.1 any Extended Maintenance subject on QOD, BIW, QW, or QOW dosing having 1 related SAE, 1 related AE graded severe, 2 related AEs occurring on separate occasions, both graded moderate, or 3 consecutive doses judged "not tolerated," will be transferred from Treatment Pathway 1 to Treatment Pathway 2 for safety reasons. Such subjects will undergo the dose reduction and modified escalation procedure described in Section 7.2.2 in order to return to a 300 mg QD regimen. Alternatively, they may be discontinued from the study.

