4.4.1 Criteria for Early Discontinuation

A subject who meets any of the following must discontinue dosing with AR101:

- 1. Pregnancy
- 2. Life-threatening symptoms (CoFAR grade 4; Appendix 9), including, but not limited to anaphylaxis resulting in hypotension, neurologic compromise, or mechanical ventilation secondary to peanut OIT dosing or any peanut food challenge
- 3. Severe allergic hypersensitivity symptoms (CoFAR grade 3; Appendix 9) that require intensive therapy (to be determined by the investigator but may include such interventions as IV epinephrine, intubation, or admission to an intensive care unit) or those that are recurrent. Subjects who experience severe symptoms (eg, severe nausea, rhinorrhea, or pruritus) that are not life-threatening, not requiring intensive therapy, and not associated with any other features indicating a serious clinical condition, and who the investigator feels are suitable to continue with the study, will be discussed with the medical monitor and may continue the study under close supervision if both the investigator and the medical monitor deem it appropriately safe to do so
- 4. Dose-limiting symptoms that occur at or before the 3 mg single dose on Initial Escalation Day 1 (Treatment Pathways 3 and 5 only)
- 5. Dose-limiting symptoms that occur on Initial Escalation Day 2 (Treatment Pathways 3 and 5 only)
- 6. Nonadherence: For subjects on a daily dose regimen, missing > 7 consecutive dosing days on any 1 occasion or missing 3 consecutive dosing days on 3 or more occasions during Up-Dosing, other than for treatment of an AE or a dispensing error
- 7. Extended dosing interruptions: For subjects on a daily dose regimen, any circumstances, including medical indications that require missed AR101 dosing for ≥ 15 consecutive days, with the exception of the voluntary 30-day hiatus for GI AEs
- 8. On 1 episode, failure to accomplish up-dosing to 300 mg AR101 daily after 3 attempts (Treatment Pathways 2 and 3 only)
- 9. On 1 dose-reduction episode, failure to identify a tolerated dose of AR101 after 3 attempts at dose reduction

- ARC008 Protocol Amend 6.0
- 10. Administration of more than 2 doses of epinephrine for the treatment of any single AR101-related allergic reaction
- 11. Subject desires to receive commercially available product

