If the subject experiences mild symptoms at the reduced dose, the procedures for responding to a dose with mild symptoms should be followed (see above). If the subject experiences moderate symptoms at the reduced dose level, the subject should return the next day and receive a further 1- or 2-step dose reduction (per investigator judgment) at the study site. If this reduced dose is well tolerated, it will be continued as the daily home dose for ≥ 2 weeks before re-escalation is attempted at the study site. If the dose is not well tolerated, but elicits mild symptoms, then the treatment procedures for responding to mild symptoms should be followed (see above). If, however, the subject again experiences moderate symptoms at the reduced dose level, a discussion with the medical monitor is to ensue to reach a decision as to whether to continue the subject in the study.

In the rare instance that a dose eliciting moderate symptoms is *assessed as tolerated*, then the actions taken should be the same as for a dose with mild symptoms *assessed as tolerated*.

• Severe symptoms (these always indicate lack of tolerability): If severe symptoms occur, the action should be to treat the subject for the allergic reaction, and then, in consultation with the medical monitor, decide whether to discontinue the subject from the study. If it is determined that it is safe to allow the subject to continue in the study, the subject should return the next day for dosing at a 2-step reduction in dose under observation at the study site. If the subject tolerates the dose reduction (ie, shows no or only mild symptoms that are assessed as tolerated), then the subject is to remain at the reduced dose level for ≥ 2 weeks before attempting dose re-escalation at the study site. If the subject does not tolerate the reduced dose, then the subject will discontinue study treatment.

Severe symptoms requiring 0 to 1 dose of epinephrine: If a subject experiences severe symptoms requiring 0 to 1 dose of epinephrine, the procedure is to have the subject return to the study site for the next dose and to reduce the dose by 2 dose levels. If no or mild symptoms (assessed as tolerable) occur, dosing may proceed at

the reduced level for at least 2 and up to 4 weeks. If moderate or severe symptoms occur, dosing is to be discontinued.

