Severe symptoms requiring ≥ 2 doses of epinephrine: If a subject experiences severe symptoms requiring ≥ 2 doses of epinephrine, the procedures outlined in the above paragraph should be followed; however, dosing will proceed at the reduced dose level (if tolerated) for at least 6 and up to 8 weeks.

For specific questions related to dose-escalation or continuation of the same dose that are not answered in the above protocol, the medical monitor will be available for consultation.

6.9.4 Management of Symptoms Related to Dosing During Up-Dosing Period After the First Dose (Treatment Pathways 2, 3, and 5)

Whereas the Initial Escalation Period occurs exclusively at the study site, most doses of AR101 will be given at home during the Up-Dosing and Maintenance Periods of ARC008. With the occurrence of symptoms of an acute reaction to AR101 after home dosing, or any acute allergic reaction, subjects or parents/caregivers are instructed to call the study site personnel. When symptoms of an allergic reaction related to dosing are reported during the course of daily home-dosing in any period, the investigator must assess the severity of the reaction and whether the dose associated with the reaction was tolerated (Table 9). Because of the reduced reliability inherent in the second-hand reporting of symptoms, investigators are strongly encouraged to have subjects return to the clinic to undergo dosing under direct observation whenever acute allergic symptoms associated with dosing are reported. If a previously tolerated dose or dose level is subsequently assessed *as not tolerated*, the action taken will depend on the type and severity of the reaction related to dosing and the investigator's clinical judgment. The following possible actions are described and also shown in Figure 10:

- Dosing the subject under medical supervision at the study site this is encouraged whenever there is question as to the tolerability of a dose level. It may be performed at the current dose level or at a reduced dose level, if there is already a high index of suspicion that the current dose level has not been tolerated.
- Holding dose level at current level for an additional 1 to 2 weeks before attempting dose escalation this may be done at the discretion of the investigator if there is concern that the current dose level has not been sufficiently well tolerated to attempt up-dosing to the next dose level.

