- Reducing dose by 1 or 2 dose levels and maintaining the reduced dose level for 2- to 4-week period before attempting dose re-escalation Generally, this should be the action taken when a dose that has been observed at the study site is assessed as not tolerated, if a dose elicits moderately severe symptoms, if a single dose of epinephrine has been administered to treat a dosing reaction, or if the investigator is convinced of the intolerability of the current dose level. In short, it should be considered the default action whenever a dose or dose level is assessed *as not tolerated*.

- Reducing dose level for less than the usual 2-week period this may be instituted as treatment for an intercurrent AE, to aid the investigator in determining if a dose level is or is not tolerated, or if a pattern of decreased study product tolerability during menses is discerned. The level of the reduction in dose, ranging from a 1-step reduction to a 50% reduction will be at the investigator's discretion, based on clinical judgment. The manner in which dose escalation may resume will depend on the level and the duration of the dose reduction.
- Temporarily withholding study product dosing this may be instituted as treatment for an intercurrent AE or to aid the investigator in determining if a dose level is or is not tolerated, but the duration of withholding study product may not exceed 14 consecutive days, or the subject will be discontinued from the study. The manner in which dosing may resume after withholding dosing of study product depends on the duration for which dosing was withheld.
- Reducing dose by 2 dose levels and maintaining the reduced dose level for ≥ 6 weeks – continuing dosing at a reduced dose level for ≥ 6 weeks prior to attempting re-escalation is mandatory if 2 doses of epinephrine are given to treat a single AE.
- Stopping dosing and discontinuing the subject early from the study this is an option that the subject may elect anytime and for any reason. The investigator must discontinue the subject from further dosing and continuation in the study under circumstances that could jeopardize the health of the subject or the integrity of the study.

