For any subject having chronic/recurrent GI symptoms, especially upper GI symptoms, investigators are advised to have a low threshold for instituting a dose reduction and/or for considering early discontinuation of affected subjects from the study even if mild, owing to the potential for EoE. Further specific instructions for this AEI are provided in Section 8.1.4.2.

Dose adjustment after administration of antihistamines and/or epinephrine for allergy symptoms related to dosing is described in Section 6.10.

6.9.5 Management of Symptoms Related to Dosing Occurring During Maintenance Period (All Treatment Pathways)

Dosing guidelines following treatments given for reactions experienced by subjects in all Treatment Pathways receiving AR101 at 300 mg QD, QOD, BIW, QW, or QOW during the Maintenance and Extended Maintenance period are summarized in Table 10. A textual explanation follows the table. Dose adjustment after administration of antihistamines and/or epinephrine for allergy symptoms related to dosing is described in Section 6.10.

Table 10: Dose Adjustments Following Symptoms Related to Dosing Experienced by Subjects Receiving AR101 at 300 mg QD, QOD, BIW, QW, or QOW During Maintenance and Extended Maintenance

Treatment Regimen	Dosing Guidelines and Procedures
QD	Use up-dosing procedures (Section 6.9.3, Section 6.9.4).
QOD, BIW, QW, or QOW	For intercurrent AEs and symptoms related to dosing, hold the scheduled dose until the AE is resolved and the dose can be safely administered.
	 Reset the interval between doses once the subsequent dose is tolerated.
	 If the dose must be held for > 3 days past when the dose was due to be taken, the investigator must discuss the case with the sponsor's medical monitor prior to administering the next dose. Dosing options are described in the text following this table.
	• Subjects may be transferred to Treatment Pathway 2 anytime if impaired tolerability of the dosing regimen develops (Section 3.1.1); and they will be transferred to Treatment Pathway 2 following the occurrence of any of the following:
	- 1 related SAE
	 1 related AE graded severe
	 2 related AEs occurring on separate occasions, both graded moderate, or
	 3 consecutive doses judged "not tolerated"

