6.10 Treatment for Dosing Reactions: Pharmacological and Supportive Therapy

Treatment for allergic reactions during the study is guided by the type of symptoms and severity as determined by the investigator.

- Treatment for acute reactions should be provided according to the standard of allergy care, with an antihistamine and/or epinephrine, along with IV fluids, a beta-agonist (eg, albuterol, by inhaler or nebulizer), oxygen, and/or glucocorticosteroids, as indicated.
 - Many mild acute allergic reactions can be transient and self-limiting, requiring no therapeutic intervention. Others, however, may require treatment. Generally, for mild symptoms requiring treatment, the subject should receive antihistamines.
- Acute allergic reactions manifesting with moderate symptoms will generally require therapeutic intervention, although some, even moderate, symptoms may on rare occasion be so transient as to require no specific treatment. Generally, for moderate symptoms requiring treatment, the subjects should receive antihistamines and/or

- ARC008 Protocol Amend 6.0
- epinephrine, as indicated. If there is uncertainty as to the severity of the reaction, administering epinephrine would be considered the most appropriate course of action.
- Generally, severe symptoms will require treatment. This will usually consist of antihistamines and/or epinephrine, as indicated. If there is uncertainty as to the severity of the reaction, administering epinephrine would be considered the most appropriate course of action.

The procedures that should be implemented after treatment of a reaction to an AR101 dose during the study are summarized in Table 11. An explanation follows the table.

Table 11: Procedures Following Treatment of a Dosing Reaction

Treatment Given for Reaction	Procedures Following Treatment
≤ 2 doses of antihistamines	Continue dose escalation if in Initial Escalation / Up-Dosing Period
Epinephrine: > 2 doses either in clinic or at home	Subject returns to clinic, undergoes Early Discontinuation visit, discontinues treatment
Epinephrine: single dose given in clinic	 Stop dosing at clinic Reduce next dose by 2 dose levels and administer in clinic Continue biweekly escalation
Epinephrine required for a second consecutive time during, or after, 1 escalation attempt	 Reduce next dose by 2 dose levels and administer in clinic Reduced dose level continued for 6 to 8 weeks Escalation may be attempted after 6 to 8 weeks

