Epinephrine required for a third consecutive time during an escalation attempt	Discontinue dosing Subject returns to clinic 14 days after last dose for Early Discontinuation visit
Epinephrine: single dose at home	Not counted in the total count of epinephrine uses unless severe anaphylaxis has occurred
	Reduce next dose by 1 or 2 dose levels and administer in clinic under medical supervision prior to resuming any dosing at home

• Antihistamines Given

If a subject receives 2 or fewer doses of antihistamines only, the dose escalation can be continued. If more than 2 doses of antihistamine, or epinephrine, or a combination of medications, is administered, then a different course of action is to be taken.

If symptoms during up-dosing at the study site or at home require > 2 doses of antihistamine alone or in combination with other medications (except epinephrine), reduce the next dose of study product by 1 or 2 dose levels and give it at the study site under medical supervision. If no symptoms occur at the reduced dose, continue up-dosing for the 2-week dosing interval.

ARC008 Protocol Amend 6.0

• Epinephrine – General Procedures

Any reaction to study product (in clinic or at home) that requires more than 2 doses of epinephrine will stop all further dosing of study product for the individual. The subject will be asked to return 14 days following the last dose of study product for an Early Discontinuation visit (Section 4.4).

• Epinephrine – Single Dose Administered at Clinic

If a single administration of epinephrine is required during, or after, a dose escalation in the clinic, no further dosing of study product is to occur at that visit. The next dose of study product is to be reduced by 2 dose levels and administered at the study site, but biweekly dose escalation should continue.

If a single administration of epinephrine is required for a second consecutive time during or after 1 escalation attempt, the dose should be reduced by 2 dose levels and the same dose level continued for 6 to 8 weeks. After 6 to 8 weeks at the reduced dose, an escalation may be attempted in the clinic.

If a single administration of epinephrine is required for a third consecutive time during an escalation attempt, no further dosing should be attempted and dosing will be discontinued. Subjects will be asked to return 14 days following their last dose of study product for an Early Discontinuation visit (Section 4.4).

• Epinephrine – Home

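### Protocol 6.9.3 continues dosing after severe reactions needing 2 or more epinephrine doses with no upper limit, which contradicts the mandatory stop after more than 2 doses in 4.4.1 and 6.10

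*Protocol*

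**What the plan says.** Section 6.9.3 divides severe up-dosing reactions into two categories. After 0 to 1 dose of epinephrine, the subject returns to the site, drops two dose levels and, if the lower dose is tolerated, stays there for 2 to 4 weeks. For the other category it says: "If a subject experiences severe symptoms requiring ≥ 2 doses of epinephrine, the procedures outlined in the above paragraph should be followed". The only change is the duration: "dosing will proceed at the reduced dose level (if tolerated) for at least 6 and up to 8 weeks".

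Section 4.4.1 lists events after which AR101 dosing must cease. Criterion 10 is: "Administration of more than 2 doses of epinephrine for the treatment of any single AR101-related allergic reaction". Section 6.10 repeats this twice. A row of Table 11 ("Epinephrine: > 2 doses either in clinic or at home") leads to discontinuation of treatment, and the text says that any reaction to study product that "requires more than 2 doses of epinephrine will stop all further dosing of study product for the individual".

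Section 6.9.4 covers symptoms after the first dose at a level. It makes a two-level reduction held for at least 6 weeks "mandatory if 2 doses of epinephrine are given to treat a single AE".

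For daily maintenance, Table 10 in Section 6.9.5 says: "Use up-dosing procedures (Section 6.9.3, Section 6.9.4".

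**The concern.** For one and the same event, a severe AR101 reaction treated with 3 or more epinephrine doses, one section tells the site to carry on at a lower dose and two others tell it to stop for good. A site working from 6.9.3 would see its case covered there, because 0 to 1 and 2 or more between them take in every possible count. Nothing in 6.9.3 signals that a third outcome exists.

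The main stake is subject safety. Many participants are children, and the instruction would re-expose a subject to the allergen after a reaction that the protocol elsewhere treats as disqualifying. There is a smaller reporting consequence. Premature discontinuation of dosing due to adverse events is one of the primary safety endpoints (Protocol Table 1; SAP 3.1), and whether such a subject is counted can depend on the section the site followed. The triggering reaction is counted as epinephrine use either way, and no other statistical figure is affected.

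**Working it through.** The plan gives no figure to reproduce here; the check compares thresholds. Let *n* be the number of epinephrine doses given for one severe AR101 dosing reaction.

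| *n* | Section 6.9.3 | Section 6.9.4 | 4.4.1 criterion 10 and 6.10 (more than 2 doses) | Result |
|---|---|---|---|---|
| 0–1 | Two levels down, 2–4 weeks | 6-week rule not triggered | Not triggered | Consistent |
| 2 | Two levels down, 6–8 weeks | Two levels down, at least 6 weeks | Not triggered | Consistent |
| 3 or more | Two levels down, 6–8 weeks | 6-week rule is stated for 2 doses | Permanent stop | Conflict |

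The continue rule covers {n ≥ 2} and the stop rule covers {n > 2}. Their overlap is {n ≥ 3}. If 6.9.3 read exactly 2, the three ranges (0–1, 2, more than 2) would be exhaustive and would not overlap.

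**Which text is wrong.** The stop at more than 2 doses appears in 4.4.1, in Table 11 and in the text of 6.10. Section 8.4.3 also uses more than 2 doses as a trigger for forwarding anaphylaxis reports to the safety team. Section 6.9.4 attaches the 6-week rule to 2 doses. The part of Figure 10 that is legible in the copy reviewed also reads 2 doses; as the figure is incomplete there, this is weak support. Section 6.9.3 is the exception, and it has the ≥ sign in both its sub-heading and its sentence.

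**Reach.** The conflict covers up-dosing in Treatment Pathways 2, 3 and 5 and, through Table 10, daily maintenance. It does not reach Initial Escalation or the nondaily regimens, which have their own rules. It also excludes events already stopped under Section 5.3 (hypoxia, hypotension, mental-status change, grade 3 anaphylaxis, intensive therapy) or under 4.4.1 criteria 2 and 3. Those rules do not close the gap: criterion 3 lets some severe reactions without intensive therapy continue, and neither 5.3 nor criterion 3 sets an epinephrine dose count.

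**Illustration for one subject at 300 mg/day.**
- Two levels down in Tables 4 and 5: 300 → 240 → 200 mg.
- Minimum: 6 weeks × 7 = 42 daily doses; 42 × 200 mg = 8,400 mg of peanut protein.
- Maximum: 8 weeks × 7 = 56 daily doses; 56 × 200 mg = 11,200 mg.
- Under the stop rule: 0 doses, 0 mg.

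**The case against.** The strongest reply is that a careful reader already knows which rule governs. Criterion 10 is mandatory, whereas 6.9.3 says its procedures should be followed. Section 6.9.3 refers the reader to 6.10 for dose adjustment after epinephrine, and the same pointer appears at the end of 6.9.4 and in 6.9.5 before Table 10. The severe-symptom rule also puts a consultation with the medical monitor first, with reduced dosing following only "If it is determined that it is safe to allow the subject to continue in the study". That is the natural point to apply the 4.4.1 criteria. Even if everyone missed them, the next dose would be supervised at the site, two levels down, and moderate or severe symptoms would end dosing. The affected group is narrow, and its size depends partly on severity definitions in appendices that were not available for this review. The milligram totals describe a subject who is tolerating the dose, so they do not measure harm.

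Much of this stands. A careful site would probably stop, the event is probably rare, and the totals only illustrate how far apart the two instructions are. But no sentence says that 4.4.1 or 6.10 takes precedence, and 6.9.3 makes no exception for more than 2 doses. The monitor step leaves to judgement what criterion 10 does not allow. The closing offer in 6.9.3 of further consultation covers only questions the text leaves unanswered, and here the text appears to give an answer.

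**Conclusion.** The concern holds. For severe AR101 reactions needing 3 or more epinephrine doses, 6.9.3 as written contradicts a mandatory safety stop stated once in 4.4.1 and twice in 6.10. At exactly 2 doses there is no conflict. The error is in 6.9.3, not in the stop rule.

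How many subjects are affected cannot be estimated, because the documents give no frequency. The difference of 42 to 56 doses assumes one subject starting at 300 mg/day, a tolerated reduction to 200 mg, no missed doses, and no other stop rule applying. The only statistical effect is on the count of discontinuations due to adverse events. The correction should be made because the wrong threshold governs re-exposure after a severe reaction; the numbers involved are likely to be small.

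**What to change.** In Section 6.9.3, change the threshold from 2 or more doses to exactly 2 doses, in both the sub-heading and the sentence. Add one line stating that after more than 2 doses dosing is discontinued under Section 4.4.1 criterion 10 and Section 6.10. Check that Figure 10 shows the same three categories. Sections 4.4.1, 6.9.4 and 6.10 need no change on this point.

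The cost is one corrected threshold, one added sentence and one figure check. No new procedure, data collection or analysis is needed.
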